- 15. Have clinical evidence of significant active hematological disease; WBC count  $\leq 2500/\mu L (2.50 \times 10^9/L)$  or an absolute neutrophil count  $\leq 1000/\mu L (1.00 \times 10^9/L)$

- 16. Have conditions that may interfere with their participation in the study and/or with the PK of study drug
- 17. Have participated in a study involving administration of an investigational drug or device within 4 weeks before Visit 1, or within approximately 5 half-lives of the previous investigational compound, whichever is longer
- 18. Have recently (within 30 days before Visit 1) been exposed to perampanel in a clinical study or by prescription, and/or previous discontinuation from perampanel treatment due to adverse events related to perampanel (revised per Amendment 02)
- 19. Have a clinically significant electrocardiogram (ECG) abnormality, including prolonged corrected QT interval (QTc) defined as > 450 msec
- 20. Have had multiple drug allergies or a severe drug reaction to an AED(s), including dermatological (eg, Stevens-Johnson syndrome), hematological, or organ toxicity reactions
- 9.3.3 Removal of Subjects From Therapy or Assessment

The investigator may withdraw the subject from the study at any time for safety or administrative reasons. The subject may stop study drug or withdraw from the study at any time for any reason.

In the event a subject discontinues study drug, an Early Discontinuation Visit will be performed. The subject should also return 4 weeks ( $\pm 6$  days) after the last dose of study drug to complete the Follow-up Visit procedures. The Subject Disposition case report form (CRF) will be completed indicating the primary reason for discontinuation and all other reasons contributing to the subject's discontinuation from treatment. In addition, the date of last dose of study drug will be recorded on the Study Drug Dosing CRF.

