#### Table 4Schedule of Procedures/Assessments in Study E2007-G000-238: Core Study – Non-EIAED Subjects

#### Table 4Schedule of Procedures/Assessments in Study E2007-G000-238: Core Study – Non-EIAED Subjects

Phase						Treatn					
Period	Pretreatment	'retreatment Titration						Maintenance		Early Discontinuation	Unscheduled
Visit	1	2 b	3 b	4 c	5°	6 c,d,e	7°	8 c,f			
Week	-2	0	2	4	8	12	14	16	20		
Days	-14	1	15	29	57	85	99	113	141		
Procedures/Assessments											

AE = Adverse event, AED = Anti-epileptic drug, CGI-C = Clinical Global Impression of Change, CGI-S = Clinical Global Impression of Severity, CLIA = Clinical Laboratory Improvement Amendments, CRF = case report form, EAP = extended access program, ECG = electrocardiogram, EOT = end of treatment, fT3 = free triiodothyronine, fT4 = free thyroxine, IGF-1 = insulin-like growth factor-1, PK = pharmacokinetics, SAE = serious adverse event, TSH = thyroid-stimulating hormone.

a: To be done within ±6 days of the scheduled visit. Visit applies only to those subjects who complete the Treatment Phase but do not roll-over into the Extension Phase and those subjects who discontinue the study early for any reason after Visit 2 and before Visit 8.

- b: To be done within  $\pm 2$  days of the scheduled visit.
- c: Visits should be done within ± 3 days of the scheduled visit. There must be at least 10 days of treatment between Visits 3 and 4, 4 and 5, and 5 and 6.
- d: Upon successful completion of Visit 6, subjects will begin the Maintenance Period of the study.
- e: No dose titration is allowed at this visit or future visits.
- f: Visit 8 will be considered the first visit of the Extension Phase for subjects who choose to continue into the Extension Phase.

g: For clinic visits other than those specified, physical and complete neurological exams, including evaluation of the cranial nerves, motor, sensory, brainstem, cerebellar, and autonomic functions, will only be performed when there is a complaint from the parent/guardian.

- h: Two measurements of height/length should be taken. Each measurement should be recorded as a separate entry on the Vital Sign CRF.
- i: Only for those subjects who roll-over into the Extension Phase.
- j: Unused study drug to be retrieved and study drug dispensed only for subject requiring dose increases at Unscheduled Visits.
- k: To include the number and type of seizures for the 4 weeks before the Pretreatment Phase.

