5.6.3 Laboratory Values

Laboratory results will be summarized using Système International (SI) units, as appropriate. For all quantitative parameters listed in protocol Section 9.7.1.8, the actual value and the change from baseline to each postbaseline visit and to the end of treatment (defined as the last on-treatment value) will be summarized by visit and by age group using descriptive statistics. Qualitative parameters listed in protocol Section 9.7.1.8 will be summarized using frequencies (number and percentage of subjects), and changes from baseline to each postbaseline visit and to end of treatment will be reported using shift tables. Percentages will be based on the number of subjects with both non-missing baseline and relevant postbaseline results.

Laboratory test results will be assigned a low/normal/high (LNH) classification according to whether the value was below (L), within (N), or above (H) the laboratory parameter's reference range. Within-treatment comparisons for each laboratory parameter will be based on 3-by-3 tables (shift tables) that compare the baseline LNH classification to the LNH classification at each postbaseline visit and at the end of treatment. Similar shift tables will also compare the baseline LNH classification for the highest and lowest value during the treatment period.

Appendix 1 (Sponsor's Grading for Laboratory Values) in Section 13.1 presents the criteria that will be used to identify subjects with treatment-emergent markedly abnormal laboratory values (TEMAVs). Except for phosphate, a TEMAV is defined as a postbaseline value with an increase from baseline to a grade of 2 or higher. For phosphate, a TEMAV was defined as a postbaseline value with an increase from baseline to a grade of 3 or higher. When displaying the incidence of TEMAVs, each subject may be counted once in the laboratory parameter high and in the laboratory parameter low categories, as applicable.

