8.2.2 Visit Windows for Safety Data

For the by-visit summaries of clinical laboratory data, vital signs, ECG, and growth parameters, visit windows will be applied to determine into which study week scheduled, unscheduled, and early discontinuation data were actually recorded, relative the first dose of study drug (Day 1). The aim of using windows for visits is to include the maximum amount of data; hence windows will split at the midpoint between visits. It gives the mapping of relative day ranges to study week, as well as the target day of a given study week. Mappings of relative day ranges to study week will be done for clinical laboratory data, vital signs, ECG data and growth parameter. Tables 1&2 below provide the mapping of relative day ranges to study week for non-AE safety variables. The on-treatment duration for laboratory, vital signs, and ECG data is considered to begin on the day of the first dose of study drug and ends 14 days after the last dose of study drug, inclusive.

		Study Day Range (Relative to First Dose of	
Study Period	Study Week	Study Drug)	Target Day
Pretreatment	Baseline	Day ≤1 ^a	≤1
Treatment (Titration)	Week 2	$2 \le Day \le 21$	15
Treatment (Titration)	Week 4	$22 \le \text{Day} \le 42$	29
Treatment (Titration)	Week 8	$43 \le Day \le 70$	57
Treatment (Titration)	Week 12	$71 \le \text{Day} \le 91$	85
Treatment (Maintenance)	Week 14	$92 \le \text{Day} \le 105$	99
Treatment (Maintenance)	Week 16	$106 \le \text{Day} \le 119$	113
Treatment (Follow-Up)	Week 99	120 or $LD \le Day \le 999^{b}$	141

 Table 1. Visit Windows – Non-EIAED Subjects

- a: All assessments at Visit 2 were to be performed prior to first dose of study drug; results from these assessments will be regarded as Pretreatment values in the analyses.
- b: The last non-missing value measured in the treatment duration will be handled as the data of EOT of the core study.
- LD = Last Dose (whichever occurs first)

Table 2. Visit Windows – EIAED Subjects

Study Period	Study Week	Study Day Range (Relative to First Dose of Study Drug)	Target Day
Pretreatment	Baseline	Day ≤1 ^a	1
Treatment (Titration)	Week 2	$2 \le Day \le 21$	15
Treatment (Titration)	Week 4	$22 \le \text{Day} \le 42$	29
Treatment (Titration)	Week 8	$43 \le Day \le 70$	57
Treatment (Titration)	Week 12	$71 \le \text{Day} \le 98$	85
Treatment (Titration)	Week 16	$99 \le \text{Day} \le 119$	113
Treatment (Maintenance)	Week 18	$120 \le \text{Day} \le 133$	127

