8.2.3 Handling of Replicate Data

For the clinical laboratory data, vital signs, ECG, growth data analyses, when there are repeated laboratory tests that occur within the same visit windows (Section 8.2.2), the following rules will be used in the by-visit summary tables:

The scheduled visit assessment will be used if there are multiple assessments.

- If there are multiple scheduled visit assessments, the scheduled assessment closest
- to the target day of the visit will be used.

- If there are 2 scheduled assessments within the same visit window that are equally
- close to the target visit data, the earlier assessment will be used.
- If there are 2 scheduled assessments on the same visit, the average will be used for that visit.

If a subject did not have a recorded observation falling within a given range of days in order to be assigned a study week, the subject's data for that study week will be regarded as missing for summarization purposes.

A subject having a TEAE coded to the same PT more than once during the study will be counted only once in the incidence calculations for that TEAE. Similarly, if a subject has more than 1 TEAE in a single SOC, the incidence will be counted only once for that SOC.

For summaries by closest relationship to study drug, if a subject had a single incident of a TEAE with a missing relationship to study drug, the subject will be counted in the 'Missing' category for that PT. If a subject had two or more TEAEs in the same SOC (or with the same PT) with different relationships to study drug, then the event with the closest relationship will be used for that subject. Subjects with missing relationship to study drug for the TEAE are counted under 'Missing' category unless the subject already has another TEAE classified as Related, in which case the subject is counted under 'Related' category.

For summaries by maximum severity, if a subject had a single incident of a TEAE with a missing severity, the subject will be counted in the 'Missing' category for that PT. If a subject had two or more TEAEs in the same SOC (or with the same PT) with different severities, then the event with the maximum severity will be used for that subject. Subjects with missing severity for the TEAE are counted under 'Missing' category unless the subject already had another AE with severe intensity, in which case subject is counted under 'Severe' category.

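### SAP Tables 1 and 2 start the off-drug Follow-up row on the last-dose day, so the end-of-drug visit of a child who stops in the Core usually fits two rows of the by-visit safety tables

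*SAP*

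**What the plan says.** SAP 8.2.2 maps laboratory, vital-sign, ECG and growth data to study weeks: "visit windows will be applied to determine into which study week scheduled, unscheduled, and early discontinuation data were actually recorded". Window boundaries are meant to fall midway between visits.

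- The last Maintenance row is Week 16, Days 106 to 119, in Table 1 (non-EIAED), and Week 20, Days 134 to 154, in Table 2 (EIAED).
- The Follow-up row (Week 99) starts at Day 120 or LD in Table 1 and at Day 155 or LD in Table 2, and runs to Day 999. Its target days are 141 and 169. The footnote reads "LD = Last Dose (whichever occurs first"), and the LD day itself is included.
- The on-treatment period for laboratory, vital-sign and ECG data "ends 14 days after the last dose of study drug, inclusive".

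SAP 8.2.3 chooses among several values inside one window: "The scheduled visit assessment will be used if there are multiple assessments", and "If there are multiple scheduled visit assessments, the scheduled assessment closest" to the target day is taken. It does not place a single value that satisfies two windows.

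In Protocol Tables 4 and 5, drug is dispensed at Visit 8 (non-EIAED) or Visit 9 (EIAED) "Only for those subjects who roll-over into the Extension Phase". Protocol 9.3.3 adds: "In the event a subject discontinues study drug, an Early Discontinuation Visit will be performed". The Follow-up Visit is 4 weeks (±6 days) after the last dose, and Protocol 9.1.2.3 makes that period drug-free.

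**The concern.** For a child who stops, days LD to LD+14 are on-treatment by one sentence of SAP 8.2.2 and Follow-up by its tables. The visits held in that span include the end-of-Maintenance visit of a completer who does not continue, and the Early Discontinuation visit.

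Laboratory, vital-sign, ECG and growth parameters are part of the secondary endpoint. Laboratory results, for example, "will be summarized by visit and by age group using descriptive statistics", with shift tables at each visit. If these visits are filed as Follow-up, the end-of-Maintenance row describes a selected group, those who chose to continue. If they are filed by week with no last-dose limit, some off-drug values are reported as Titration or Maintenance values. Two programmers working from this text could produce different tables.

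**Working it through.** **1. The plan's own cut points.** Take midpoints of adjacent target days.
- Table 2 targets 15, 29, 57, 85, 113, 127, 141, 169 give 22, 43, 71, 99, 120, 134, 155. All seven match the stated row starts.
- Table 1 targets 15, 29, 57, 85, 99, 113, 141 give 22, 43, 71, 92, 106, 127. The first five match. The last is (113 + 141)/2 = 127, but the table uses 120.

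**2. Where the end-of-drug visit falls.** Follow-up applies when Day ≥ min(120, LD), or min(155, LD) for EIAED. Dosing is at bedtime under 24 months, so LD is about the visit day minus 1. At ages 2 to under 4 years the Maintenance PK-visit dose is given in clinic, so LD can be the visit day.

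| Visit | Days (±3) | LD | Rows satisfied |
|---|---|---|---|
| Visit 8, non-EIAED | 110 to 116 | same day or day before | Week 16 and Week 99 |
| Visit 9, EIAED | 138 to 144 | same day or day before | Week 20 and Week 99 |

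For Early Discontinuation visits the protocol sets no interval after LD, so a range is assumed. At LD to LD+7, 895 of 895 (non-EIAED) and 1,119 of 1,119 (EIAED) combinations of LD and visit day fit two rows. At LD to LD+14 the counts are 1,651 of 1,679 and 2,099 of 2,099. The 28 exceptions fall on or after Day 120 and fit only Week 99.

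**3. Follow-up row first.** The end-of-drug value moves to Week 99 and competes there with the actual Follow-up Visit.
- Example: Visit 8 on Day 113 with LD 112 is 141 − 113 = 28 days from target. A Follow-up Visit at LD+28 = Day 140 is 1 day away and is kept.
- Over LD 1 to 116 (non-EIAED) or 1 to 144 (EIAED), with 15 end-visit offsets (0 to 14 days) and 13 Follow-up offsets (22 to 34 days), the Follow-up Visit is closer in all 116 × 15 × 13 = 22,620 and all 144 × 15 × 13 = 28,080 combinations.
- Height and head circumference are not measured at Follow-up, so their end-of-drug values would simply appear under Follow-up.
- With the half-lives in Protocol 9.4.1 (about 25 h with an EIAED, 105 h without; not given by age), the fraction of drug left one day after LD is 2^(−24/25) = 0.51 to 2^(−24/105) = 0.85. These are not off-drug values.

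**4. Week rows first, with no last-dose limit.** Completers who stop are filed correctly: their Follow-up Visit, nominally Day 140 or 168, fits only Week 99. An early stopper's Follow-up Visit enters a week row when:
- non-EIAED: LD + 28 ≤ 119, so LD ≤ 91 (97 for a visit at LD+22, 85 at LD+34);
- EIAED: LD + 28 ≤ 154, so LD ≤ 126 (132 and 120).

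Example: with LD 57, the Follow-up Visit on Day 85 is counted as Week 12 Titration. On the 105 h half-life, 2^(−672/105) = 0.012 of the drug remains.

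**5. Moving the Follow-up start alone.** Starting Follow-up at LD+15 while Week 16/20 still ends at Day 119/154 leaves values within LD+14 but on or after Day 120/155 in no row. That is 1 + 2 + … + 11 = 66 of 116 × 15 = 1,740 combinations (LD 106 to 116) and 1 + 2 + 3 + 4 = 10 of 144 × 15 = 2,160 (LD 141 to 144). The last week row must therefore be extended as well.

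**The case against.** The best defence is that SAP 8.2.2 already holds the answer. If week rows take on-treatment data first, up to LD+14, a Follow-up Visit at LD+22 to LD+34 cannot enter a week row. That stands, and the fix uses it. But the SAP does not apply the limit to the rows, and its footnote points the other way. Applied to every row, the limit would also remove the Follow-up Visit from Week 99.

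The precedence rule may be in the programming specifications or table shells, which SAP 9 and 11 place in separate documents. This cannot be excluded, but those documents would have to override the stated boundary rather than fill in a detail.

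The harm is limited. The last on-treatment value is kept as EOT, and EOT is summarised for laboratory data, ECG interpretation and growth. The by-visit tables are descriptive, without tests. Both points stand.

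A reader might infer that every child who stops is misfiled and that no order of precedence could work. The documents do not support either:
- Protocol 9.4.1 and SAP 8.1.2 allow for tapering, so an end visit can precede the last dose.
- Visits on or after Day 120/155 fit only Week 99.
- Children who move to commercial drug or extended access have no Follow-up Visit, so their value is mislabelled but not displaced.
- Week-rows-first goes wrong only for early stoppers.

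A reader might also infer that the end-of-Maintenance row would be empty. That needs LD to mean the last Core dose for Extension entrants too, and the SAP does not say so.

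**Conclusion.** The point holds as a defect in the visit-window rule. On its plain reading the SAP files as Follow-up the end-of-Maintenance visit of completers who stop, and Early Discontinuation visits on or after the last dose, and lets the later Follow-up Visit replace them. The Week 16/20 row is then left essentially to Extension entrants. The opposite order is correct for completers but, with no last-dose limit, puts off-drug values of early stoppers into on-drug weeks.

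The effect is confined to by-visit laboratory, vital-sign, ECG and growth tables. The primary PK analysis, EOT summaries, markedly-abnormal-laboratory counts and QTcF categories do not use these rows.

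The documents do not say how many children will stop in the Core, so the total effect cannot be sized. In an age cohort at its planned minimum of 6 or 5 (Protocol synopsis, set for evaluable PK data), one child is 1/6 = 17% or 1/5 = 20% of the row. The results assume visits within protocol windows and an end visit at LD to LD+14.

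**What to change.** In SAP 8.2.2, before programming:

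1. Define LD as the last dose in the Core, and apply the LD rule only to children who do not enter the Extension.
2. For those children, let week rows take values through LD+14 and start the Follow-up row at LD+15.
3. For the same children, extend Week 16 (non-EIAED) or Week 20 (EIAED) to LD+14 where that is later than the row's fixed end, so that no value falls between rows.
4. Set the fixed Table 1 cut to Day 127, making Week 16 Days 106 to 126, as the midpoint rule requires. Table 2 keeps Day 155.
5. State that the LD+14 limit also covers growth parameters, which the on-treatment sentence does not name.

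Each value from LD to LD+14 then falls in one study week, and each Follow-up Visit (LD+22 to LD+34) only in Follow-up. The cost is a boundary edit in two tables, with no new data. Values later than LD+14 move to Follow-up.

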8.2.3 Handling of Replicate Data

For the clinical laboratory data, vital signs, ECG, growth data analyses, when there are repeated laboratory tests that occur within the same visit windows (Section 8.2.2), the following rules will be used in the by-visit summary tables:

The scheduled visit assessment will be used if there are multiple assessments.

- If there are multiple scheduled visit assessments, the scheduled assessment closest
- to the target day of the visit will be used.

- If there are 2 scheduled assessments within the same visit window that are equally
- close to the target visit data, the earlier assessment will be used.
- If there are 2 scheduled assessments on the same visit, the average will be used for that visit.

If a subject did not have a recorded observation falling within a given range of days in order to be assigned a study week, the subject's data for that study week will be regarded as missing for summarization purposes.

A subject having a TEAE coded to the same PT more than once during the study will be counted only once in the incidence calculations for that TEAE. Similarly, if a subject has more than 1 TEAE in a single SOC, the incidence will be counted only once for that SOC.

For summaries by closest relationship to study drug, if a subject had a single incident of a TEAE with a missing relationship to study drug, the subject will be counted in the 'Missing' category for that PT. If a subject had two or more TEAEs in the same SOC (or with the same PT) with different relationships to study drug, then the event with the closest relationship will be used for that subject. Subjects with missing relationship to study drug for the TEAE are counted under 'Missing' category unless the subject already has another TEAE classified as Related, in which case the subject is counted under 'Related' category.

For summaries by maximum severity, if a subject had a single incident of a TEAE with a missing severity, the subject will be counted in the 'Missing' category for that PT. If a subject had two or more TEAEs in the same SOC (or with the same PT) with different severities, then the event with the maximum severity will be used for that subject. Subjects with missing severity for the TEAE are counted under 'Missing' category unless the subject already had another AE with severe intensity, in which case subject is counted under 'Severe' category.

9 PROGRAMMING SPECIFICATIONS

The rules for programming derivations and dataset specifications are provided in separate documents.

10 STATISTICAL SOFTWARE

All statistical analyses and summaries will be performed using SAS v 9.3 or later.

11 MOCK TABLES, LISTINGS, AND GRAPHS

The study TLG shells will be provided in a separate document, which will show the content and format of all tables, listings, and graphs in detail.

13 APPENDICES

13.1 Sponsor's Grading for Determining Markedly Abnormal Laboratory Results

The following table is of Sponsor's Grading for Laboratory Values from the study protocol, Appendix 1.

	Grade 1	Grade 2	Grade 3	Grade 4
BLOOD/BONE MARROW				
Hemoglobin	<lln 10.0="" dl
<lln 100="" g="" l
<lln 6.2="" l<="" mmol="" td="" –=""><10.0 - 8.0 g/dL <100 - 80 g/L <6.2 - 4.9 mmol/L	<8.0 g/dL <80 g/L <4.9 mmol/L; transfusion indicated	life-threatening consequences; urgent intervention indicated	</lln></lln></lln>	<10.0 - 8.0 g/dL <100 - 80 g/L <6.2 - 4.9 mmol/L	<8.0 g/dL <80 g/L <4.9 mmol/L; transfusion indicated	life-threatening consequences; urgent intervention indicated
Leukocytes (total WBC)	<lln -="" 3.0×109/L <lln -="" 3000="" mm3</lln></lln>	$ \begin{array}{l} <3.0-2.0{\times}10^9/L \\ <3000-2000/mm^3 \end{array} $	$ \begin{array}{l} <2.0-1.0{\times}10^9/L \\ <2000-1000/mm^3 \end{array} $	<1.0×10 ⁹ /L <1000/mm ³
Lymphocytes	<lln -="" 800="" mm3 <lln -="" 0.8×109/L</lln></lln>		<500 - 200/mm ³ <0.5 - 0.2×10 ⁹ /L	<200/mm ³ <0.2×10 ⁹ /L
Neutrophils	<lln -="" 1.5×109/L <lln -="" 1500="" mm3</lln></lln>	$<1.5 - 1.0 \times 10^{9}/L$ $<1500 - 1000/mm^{3}$	$ \begin{array}{l} <1.0-0.5{\times}10^9/L \\ <1000-500/mm^3 \end{array} $	<0.5×10 ⁹ /L <500/mm ³
Platelets	<lln -="" 75.0×109/L <lln -="" 75,000="" mm3</lln></lln>	$ \begin{array}{l} <75.0-50.0{\times}10^9{/L} \\ <75,000-50,000{/mm^3} \end{array} $	<50.0 - 25.0×10 ⁹ /L <50,000 - 25,000/mm ³	<25.0×10 ⁹ /L <25,000/mm ³
METABOLIC/LABORATORY				
Albumin, serum- low (hypoalbuminemia)	<lln 3="" dl
<lln 30="" g="" l<="" td="" –=""><3 - 2 g/dL <30 - 20 g/L	<2 g/dL <20 g/L	life-threatening consequences; urgent intervention indicated	</lln></lln>	<3 - 2 g/dL <30 - 20 g/L	<2 g/dL <20 g/L	life-threatening consequences; urgent intervention indicated
Alkaline phosphatase	>ULN-3.0×ULN	>3.0-5.0×ULN	>5.0-20.0×ULN	>20.0×ULN
ALT	>ULN-3.0×ULN	>3.0-5.0×ULN	>5.0-20.0×ULN	>20.0×ULN
AST	>ULN-3.0×ULN	>3.0-5.0×ULN	>5.0-20.0×ULN	>20.0×ULN
Bilirubin (hyperbilirubinemia)	>ULN-1.5×ULN	>1.5-3.0×ULN	>3.0-10.0×ULN	>10.0×ULN
Calcium, serum-low (hypocalcemia)	<lln -="" 8.0="" dl
<lln -="" 2.0="" l<="" mmol="" td=""><8.0 - 7.0 mg/dL <2.0 - 1.75 mmol/L	<7.0 – 6.0 mg/dL <1.75 – 1.5 mmol/L	<6.0 mg/dL <1.5 mmol/L	</lln></lln>	<8.0 - 7.0 mg/dL <2.0 - 1.75 mmol/L	<7.0 – 6.0 mg/dL <1.75 – 1.5 mmol/L	<6.0 mg/dL <1.5 mmol/L
Calcium, serum-high (hypercalcemia)	>ULN - 11.5 mg/dL >ULN - 2.9 mmol/L	>11.5 - 12.5 mg/dL >2.9 - 3.1 mmol/L	>12.5 - 13.5 mg/dL >3.1 - 3.4 mmol/L	>13.5 mg/dL >3.4 mmol/L
Cholesterol, serum-high (hypercholesterolemia)	>ULN - 300 mg/dL >ULN - 7.75 mmol/L	>300 - 400 mg/dL >7.75 - 10.34 mmol/L	>400 - 500 mg/dL >10.34 - 12.92 mmol/L	>500 mg/dL >12.92 mmol/L
Creatinine	>ULN-1.5×ULN	>1.5-3.0×ULN	>3.0-6.0×ULN	>6.0×ULN
GGT (γ-glutamyl transpeptidase)	>ULN-3.0×ULN	>3.0-5.0×ULN	>5.0-20.0×ULN	>20.0×ULN
Glucose, serum-high (hyperglycemia)	Fasting glucose value: >ULN – 160 mg/dL >ULN – 8.9 mmol/L	Fasting glucose value: >160 – 250 mg/dL >8.9 – 13.9 mmol/L	>250 – 500 mg/dL; >13.9 – 27.8 mmol/L; hospitalization indicated	>500 mg/dL; >27.8 mmol/L;

Sponsor's Grading for Laboratory Values

Sponsor's Grading for Laboratory Values

	Grade 1	Grade 2	Grade 3	Grade 4
				life-threatening consequences
Glucose, serum-low (hypoglycemia)	<lln 55="" dl
<lln 3.0="" l<="" mmol="" td="" –=""><55 – 40 mg/dL <3.0 – 2.2 mmol/L	<40 – 30 mg/dL <2.2 – 1.7 mmol/L	<30 mg/dL <1.7 mmol/L life-threatening consequences; seizures	</lln></lln>	<55 – 40 mg/dL <3.0 – 2.2 mmol/L	<40 – 30 mg/dL <2.2 – 1.7 mmol/L	<30 mg/dL <1.7 mmol/L life-threatening consequences; seizures
Phosphate, serum-low (hypophosphatemia)	<lln 2.5="" dl
<lln 0.8="" l<="" mmol="" td="" –=""><2.5 – 2.0 mg/dL <0.8 – 0.6 mmol/L	<2.0 – 1.0 mg/dL <0.6 – 0.3 mmol/L	<1.0 mg/dL <0.3 mmol/L life-threatening consequences	</lln></lln>	<2.5 – 2.0 mg/dL <0.8 – 0.6 mmol/L	<2.0 – 1.0 mg/dL <0.6 – 0.3 mmol/L	<1.0 mg/dL <0.3 mmol/L life-threatening consequences
Potassium, serum-high (hyperkalemia)	>ULN – 5.5 mmol/L	>5.5 - 6.0 mmol/L	>6.0 – 7.0 mmol/L hospitalization indicated	>7.0 mmol/L life-threatening consequences
Potassium, serum-low (hypokalemia)	<lln -="" 3.0="" l<="" mmol="" td=""><lln 3.0="" l;
symptomatic; intervention indicated</lln>	<3.0 – 2.5 mmol/L hospitalization indicated	<2.5 mmol/L life-threatening consequences	</lln>	<lln 3.0="" l;
symptomatic; intervention indicated</lln>	<3.0 – 2.5 mmol/L hospitalization indicated	<2.5 mmol/L life-threatening consequences
Sodium, serum-high (hypernatremia)	>ULN – 150 mmol/L	>150 – 155 mmol/L	>155 – 160 mmol/L hospitalization indicated	>160 mmol/L life-threatening consequences
Sodium, serum-low (hyponatremia)	<lln 130="" l<="" mmol="" td="" –="">N/A	<130 – 120 mmol/L	<120 mmol/L life-threatening consequences	</lln>	N/A	<130 – 120 mmol/L	<120 mmol/L life-threatening consequences
Triglyceride, serum-high (hypertriglyceridemia)	150 – 300 mg/dL 1.71 – 3.42 mmol/L	>300 - 500 mg/dL >3.42 - 5.7 mmol/L	>500 – 1000 mg/dL >5.7 – 11.4 mmol/L	>1000 mg/dL >11.4 mmol/L life-threatening consequences
Uric acid, serum-high (hyperuricemia)	>ULN – 10 mg/dL ≤0.59 mmol/L without physiologic consequences	N/A	>ULN – 10 mg/dL ≤0.59 mmol/L with physiologic consequences	>10 mg/dL >0.59 mmol/L life-threatening consequences

ALT = alanine aminotransferase (serum glutamic pyruvic transaminase), AST = aspartate aminotransferase (serum glutamic oxaloacetic transaminase), LLN = lower limit of normal, ULN = upper limit of normal, WBC = white blood cell.

Based on Common Terminology Criteria for Adverse events (CTCAE) Version 4.0. Published: May 28, 2009 (v4.03: June 14, 2010).

